10.1 Adverse Events

Adverse events will be assessed according to the Common Terminology Criteria for Adverse Events (CTCAE) version 4.0 and recorded on the CRF. If CTCAE grading does not exist for an adverse event, the severity of mild, moderate, severe, and life-threatening, corresponding to Grades 1 - 4, will be used. CTCAE Grade 5 (death) will not be used in this study; rather, information about deaths will be collected through both the “Study evaluation completion – core” form or the “Study evaluation completion – extension phase” form and “Adverse Event” form. Table and listing of deaths will be created based on the “Adverse Event” form primarily including all reported adverse events with “fatal” outcome indicating end date of adverse event as date of death. Fatal adverse events will be flagged appropriately indicating if the adverse event ended within the 56-day window after end of study treatment. In case of missing adverse event end date, death will be considered as occurring within 56 days from last treatment day. A supplementary listing will also be added created based on “Study evaluation completion – core” form or the “Study evaluation completion – extension phase” forms displaying information related to study discontinuation if death was reported to be the reason for discontinuation. **Treatment-emergent** AEs (TEAEs) are AEs that started or worsened during the on-treatment period. Adverse event tables will include only TEAEs. All safety data (including those from the pre and post-treatment periods) will be listed and those collected during the pre-treatment and post-treatment period will be flagged.

Adverse events will be coded using the most recent version of the medical dictionary for regulatory activities (MedDRA) available at the time of each analysis. The incidence of all grades of treatment-emergent adverse events and grades 3 or 4 TEAEs will be summarized by system organ class only and by system organ class and preferred term for all TEAEs regardless of study drug relationship, as well as by system organ class and preferred term for serious treatment-emergent AEs regardless of study drug relationship, TEAEs suspected to be related to study drug (related to Pasireotide LAR, related to Everolimus, related to both and/or undistinguishable), for TEAEs requiring dose adjustment or study drug interruption and for TEAEs leading to study drug discontinuation separately. Non-serious TEAEs will be tabulated for preferred terms and system organ classes with >5% recorded in any treatment group. Incidence of TEAEs will also be summarized by system organ class, preferred term and maximum severity (based on CTC grades) for all TEAEs, for those related to study drug and for serious TEAEs separately. On treatment deaths will also be tabulated using system organ class and preferred term. In all summaries, at each level of summarization (system organ class, preferred term) patients will only be counted once regardless of how many times it has occurred.

For the legal requirements of ClinicalTrials.gov and EudraCT, two required tables on non-serious TEAEs with an incidence $\geq 5\%$ and on serious TEAEs, deaths and SAEs suspected to be related to study treatment will be provided by system organ class and preferred term.

If for the same patient, several consecutive AEs (irrespective of study treatment causality, seriousness and severity) occurred with the same system organ class and preferred term:

- a single occurrence will be counted if there is <1 day gap between the end date of the preceding AE and the start date of the consecutive AE
- more than one occurrence will be counted if there is >1 day gap between the end date of the preceding AE and the start date of the consecutive AE.

For occurrence, the presence of at least one SAE/ SAE suspected to be related to study treatment/ non SAE has to be checked in a block e.g. among AEs in a ≤ 1 day gap block, if at least one SAE is occurring then one occurrence is calculated for that SAE.

The number of deaths resulting from SAEs suspected to be related to study treatment and SAEs irrespective of study treatment relationship will be provided by system organ class and preferred term.

All information pertaining to the AE noted during the study will be listed by treatment group and patient, detailing verbatim given by the investigator, the preferred term, the abbreviated system organ class, start date, end date, duration, severity (CTCAE grade), relationship to study drug (not suspected, suspected to be related to SOM, suspected to be related to RAD, suspected to be related to both and/or undistinguishable), action taken (none, dose adjusted, temporarily interrupted, permanently discontinued, unknown, not applicable) and outcome (recovered, recovering/resolving, recovered/resolved with sequelae, not recovered/resolved, fatal, unknown). The AE onset will also be displayed relative (in number of days) to the day of the first dose of study medication. AEs occurring before start of study drug or 57 or more days after the discontinuation of study medication will not be considered as treatment-emergent and will not be included in AE summary tables but will be listed only. This listing will be repeated for the subsets of serious TEAEs, TEAEs leading to study drug discontinuation and TEAEs requiring dose adjustment or study drug interruption.

All deaths will be listed by treatment group and patient detailing principal cause given by the investigator, the preferred term the date of last dose and the date of death. The day of last dose and day of death will also be displayed relative to the day of the first dose of study medication. The number of days since last dose will also be presented, calculated as death day – day of last dose + 1.

Grouping of adverse events of special interest

Specific groupings of adverse events of special interest will be considered and the number of patients with at least one event in each grouping will be reported. Such groups consist of adverse events for which there is a specific clinical interest in connection with everolimus or pasireotide treatment (i.e. where everolimus or pasireotide may influence a common mechanism of action responsible for triggering them) or adverse events which are similar in nature (although not identical).

Adverse event groupings can be defined through e.g. the use of Preferred Terms (PT), High Level Terms (HLT) or System Organ Classes (SOC) or through a combination of these three components.

Adverse event groupings will be performed by Novartis and the created adverse event risk analysis dataset will be forwarded [REDACTED] to generate summary tables. Summaries of the adverse events of special interest by specific grouping term and preferred term will be produced. These summaries will be repeated for adverse event groupings related to everolimus and pasireotide treatment separately. These will be produced for all adverse events of special interest regardless of study drug relationship as well as for adverse events of special interest suspected to be related to study drug including summaries for all CTC grades and CTC grades 3 or 4.

10.2 Laboratory values

All laboratory values will be converted into SI units; for laboratory tests covered by the CTCAE version 4.0 (see National Cancer Institute (NCI) 2009), the study's biostatistical and reporting team will grade laboratory data accordingly. For laboratory tests covered by CTCAE, a Grade 0 will be assigned for all non-missing values not graded as 1 or higher. Grade 5 will not be used. For laboratory tests where grades are not defined by CTCAE, results will be graded by the low/normal/high classifications based on laboratory normal ranges.

All summaries will be produced separately for each lab category (hematology, biochemistry and urinalysis). Hematology includes hemoglobin, hematocrit, platelets and total white blood cell count (WBC, absolute & differential including neutrophils, lymphocytes, monocytes, eosinophils and basophils). Biochemistry includes sodium, potassium, chloride, bicarbonate, creatinine, total protein, uric acid, blood urea nitrogen (BUN), calcium, magnesium and phosphate. Urinalysis includes pH, protein, glucose, blood, ketones and leukocytes. They will be tested using a dipstick. In some cases urea results will be collected rather than BUN. In these cases urea will be converted to BUN using the following conversions:

$$\text{BUN (mg/dL)} = \text{Urea (mg/dL)} / 2.14$$

$$\text{BUN (mmol/L)} = \text{Urea (mmol/L)} / 2$$

Shift tables using CTCAE grades will be produced for hematology and biochemistry separately to compare baseline and the worst on-treatment value with each laboratory parameter on a new page. Percentages will be calculated using the number of available patients at baseline with corresponding grade and at least one non-missing post baseline value as the denominator.

For laboratory tests where CTCAE grades are not defined, shift tables using the low/normal/high/(low and high) classification will be produced to compare baseline to the worst on-treatment value with each laboratory parameter on a new page. Percentages will be calculated using the number of available patients at baseline with corresponding level and at least one non-missing post baseline value as the denominator.

The following rules will be applied to derive the WBC differential counts when only percentages are available (this is mainly important for neutrophils and lymphocytes, as the CTC grading is based on the absolute counts).

The method to convert the value is as follows: for each patient, the original laboratory value (%) is divided by 100 and multiplied by the WBC count, e.g. for neutrophils (NEU):

NEU count = (WBC count) * (NEU %value / 100)

In order to derive the corresponding absolute normal range, the rule to be applied depends on the availability of the % range and the absolute range for the differential:

- If the % range is missing and the absolute range is missing, then the pre-defined normal range as reported in the Merck manual (FRM-0015557 Laboratory value references) will be used.
- If the absolute range is NOT missing (% range is or isn't missing), then the absolute range provided by the site will be used.
- If the % range is NOT missing and the absolute range is missing, then the % normal limits (i.e. lower limit normal (LLN) and upper limit normal (ULN)) are divided by 100 and multiplied by the corresponding normal limits of WBC count, e.g. for NEU:

LLN for NEU count = (LLN for WBC count) * (LLN for NEU % value/ 100)

ULN for NEU count = (ULN for WBC count) * (ULN for NEU % value / 100)

A listing will be presented for all hematology, biochemistry and urinalysis laboratory data, with values flagged to show the corresponding CTCAE grades and the classifications relative to the laboratory normal ranges. A separate listing will be created presenting the laboratory normal ranges for the collected parameters by laboratory identification number and laboratory group.

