7.2.2.5.3 Biochemistry

The following tests will be performed at each scheduled visit (± 7 days during monthly visit period and ± 2 days during the weekly visit period) as indicated in [Table 7-1](#) and in [Table 7-2](#) and will include sodium, potassium, chloride, bicarbonate, creatinine, total protein, uric acid, BUN (or urea, if BUN cannot be directly evaluated), calcium, magnesium, phosphate. If the biochemistry tests of Visit 1 have been done less than 7 days before treatment start, they should not be repeated on Cycle 1 Day 1.

One pre-dose, blood draw for plasma ACTH will be taken at visit 1 (baseline). In patients with ACTH hypersecretion at baseline, ACTH will be tested during the study every 3 month (± 7 days).

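### SAP 10.2 divides urea in mmol/L by 2 to obtain BUN, which cannot be reconciled with its own mg/dL divisor of 2.14

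*SAP*

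**What the plan says.** Protocol 7.2.2.5.3 lists the biochemistry panel and allows a substitute for one analyte: "BUN (or urea, if BUN cannot be directly evaluated"). SAP 10.2 takes this up ("In some cases urea results will be collected rather than BUN") and states that "urea will be converted to BUN using the following conversions", one per unit:

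- BUN (mg/dL) = urea (mg/dL) / 2.14
- BUN (mmol/L) = urea (mmol/L) / 2

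The same section opens with a general rule: "All laboratory values will be converted into SI units". It does not say whether a urea result in mg/dL is turned into BUN first and into SI units afterwards, or the reverse.

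For tests without a CTCAE grade, SAP 10.2 states that "results will be graded by the low/normal/high classifications based on laboratory normal ranges", and shift tables and a listing follow from that. For white-cell differentials the section sets out how the lower and upper normal limits are derived alongside the converted value. For urea it gives no such rule.

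**The concern.** The two lines describe the same quantity in two units, so one sample should give one BUN whichever line is used. The factor 2.14 is the ratio of the mass of urea to the mass of the nitrogen in it. A molar formula has no reason to carry that ratio: one urea molecule holds two nitrogen atoms, so in mmol/L the BUN figure either equals the urea figure (counted per molecule) or is twice it (counted per atom). Division by 2 goes in the opposite direction from the second convention and does not match the first.

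At stake are the BUN values in the biochemistry listing and, depending on how normal ranges are treated, the low/normal/high classes in the BUN shift table.

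**Working it through.** **Inputs.** From SAP 10.2: divisor 2.14 for mg/dL, divisor 2 for mmol/L. Not in the documents, assumed from basic chemistry: urea 60.06 g/mol, nitrogen 14.007 g/mol, two nitrogens per urea molecule (28.01 g/mol).

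**Step 1: reproduce the mg/dL line.** 60.06 / 28.01 = 2.144. The SAP's 2.14 reproduces.

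**Step 2: one sample by both routes.** Take urea 60 mg/dL.

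- In molar units: 60 × 10 / 60.06 = 9.99 mmol/L urea.
- mg/dL line: 60 / 2.14 = 28.04 mg/dL BUN.
- In mmol/L per urea molecule: 28.04 × 10 / 28.01 = 10.0.
- In mmol/L per nitrogen atom: 28.04 × 10 / 14.007 = 20.0.
- mmol/L line: 9.99 / 2 = 5.0.

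| Convention for BUN in mmol/L | Implied by the 2.14 line | SAP mmol/L line | Ratio | Divisor consistent with 2.14 |
|---|---|---|---|---|
| Per urea molecule | 10.0 | 5.0 | 0.50 | 9.99 / 10.0 = 1.0 |
| Per nitrogen atom | 20.0 | 5.0 | 0.25 | 9.99 / 20.0 = 0.5 |

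The ratios do not depend on the concentration: urea 30 and 120 mg/dL give the same 0.50 and 0.25. Rounded masses (60 and 28) also change nothing.

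**Step 3: could any convention give a divisor of 2?** Setting (urea / 2.14) × 10 / M equal to (urea × 10 / 60.06) / 2 gives M = 60.06 × 2 / 2.14 = 56.1 g/mol. The BUN unit would have to weigh 56.1 g/mol, about four nitrogen atoms. Neither 28.01 nor 14.007 fits.

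**Step 4: effect on low/normal/high.** Let L and U be the laboratory's lower and upper limits for urea.

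- Value and limits both divided by 2: urea/2 > U/2 exactly when urea > U. The class is unchanged.
- Value divided by 2, limits left as they are: the result is high only if urea > 2U, and is low whenever urea < 2L. Classes shift downward.
- Value divided by 2 and compared with a correct BUN range: the same thresholds per urea molecule. Per nitrogen atom the range is 2L to 2U, so the result is high only if urea > 4U and low if urea < 4L.

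Which case applies cannot be read from the SAP.

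**The case against.** The strongest reply concedes the divisor and contests the reach. Several larger readings are tempting, and the documents do not support them.

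- **That BUN is halved at every site reporting urea.** The SAP has a separate, correct mg/dL line. Results converted there are right unless they are first turned into mmol/L urea and then divided by 2. The general SI rule does not settle the order, and converting to BUN first is at least as natural. The number of urea-reporting sites and their units are not given.
- **That halved values are averaged with directly measured BUN.** SAP 10.2 plans shift tables and listings for biochemistry, not means or change-from-baseline summaries. Centres are combined within arm, but what is combined in the shift table is category counts.
- **That raised values will be classed normal.** This depends on the range handling in step 4. The parallel treatment of limits for white-cell differentials suggests that it could be done for urea, without showing that it is.
- **That renal toxicity could be hidden.** Protocol 1.2.2.3 does name renal failure as a serious everolimus risk. However, creatinine is collected and analysed separately, and Protocol 7.2.2.5 and 8.1.2.1 have clinically relevant abnormalities recorded as adverse events at the site. The conversion is an analysis step and does not alter what the investigator sees.
- **That 2 against 2.14 is a contradiction on its face.** It is not: mass and molar factors need not be equal. The conflict appears only after unit conversion with the assumed molar masses.

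All of these limits stand. None of them rescues the mmol/L line.

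**Conclusion.** The mmol/L formula is wrong as written. Under standard molar masses it is incompatible with the SAP's own mg/dL formula, whichever molar convention is meant. Any urea result converted by it gets 50% (per urea molecule) or 25% (per nitrogen atom) of the BUN that the 2.14 line implies.

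The certain consequence is wrong BUN values in the listing for those results. A downward shift of low/normal/high classes is possible and turns on whether the range is divided by the same factor; it also presumes that BUN falls under the normal-range classification rather than a CTCAE grade. The number of affected results cannot be estimated from the documents. The error is confined to one safety analyte and has no bearing on the primary or other efficacy endpoints, on creatinine or on adverse event reporting.

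**What to change.** In SAP 10.2:

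1. Replace the mmol/L divisor so that it agrees with the 2.14 line: factor 1 if BUN is expressed per urea molecule, or multiply by 2 if expressed per nitrogen atom. State which convention is used.
2. State the order of operations, for example that mg/dL urea is converted to mg/dL BUN and only then to SI units.
3. State that the laboratory's urea normal range is converted with the same factor as the value before low/normal/high classification.
4. Re-run the BUN shift table and the BUN entries in the biochemistry listing.

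The cost is one corrected formula, two or three added sentences and one analyte's outputs. Because SAP section 10 already repeats all safety outputs on cumulative core and extension data, the correction can be made in that run.

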10.3 Hepatitis screening and evaluation

In certain instances, patients must be tested for Hepatitis B viral load and serologic markers, that is, HBV-DNA, HBsAg, HBsAb, and HBcAb as well as Hepatitis C. These instances are described in the protocol.

For the parameter of HBV-DNA where the result is recorded as negative, positive or not done at multiple visits, frequencies of these results will be produced for baseline and each post-baseline visit. Percentages will be calculated using the number of available patients at that visit, for the particular treatment group. A similar table will be produced for the HCV RNA-PCR parameter.

For the parameters of HBsAg, HBsAb and HBcAb where the result is recorded as negative, positive or not done at baseline only, the frequencies of these results will be produced by treatment.

A listing will be presented by treatment showing the visit, sample date, laboratory number, laboratory name, HBV-DNA (negative, positive, not done), HBsAg (negative, positive, not done), HBsAb (negative, positive, not done), HBcAb (negative, positive, not done) and HCV RNA-PCR (negative, positive, not done). HBV-DNA and HCV RNA-PCR are the only tests carried out post-baseline and only in certain circumstances.

10.4 Liver function tests

The liver function tests carried out will be albumin, serum glutamic oxaloacetic transaminase (aspartate aminotransferase) (SGOT (AST)), serum glutamic pyruvic transaminase SSC

(alanine aminotransferase) (SGPT (ALT)), total bilirubin (fractionate to direct/indirect bilirubin if total bilirubin is $> 2.0 \times \text{ULN}$), alkaline phosphatase and gamma-glutamyl transpeptidase (GGT). For patients treated with pasireotide LAR: the Day 21 and Day 49 liver function tests should be available and assessed prior to dosing on Day 29 (2nd LAR injection) and Day 57 (3rd LAR injection). The coagulation parameters of international normalized ratio (INR) will be determined at baseline, at Visits 2, 5, 7, 8, then every 8 weeks in the core study and every 3 months in the extension phase. It will be determined also at Visits 4 and 6 for patients treated with pasireotide LAR. The partial thromboplastin time (PTT) will be determined only at baseline.

A shift table using CTCAE grades will be produced for these parameters, with the exception of PTT as it is captured as baseline only, to compare baseline and the worst on-treatment value with each laboratory parameter on a new page. Percentages will be calculated using the number of available patients at baseline with corresponding grade and at least one non-missing post baseline value as the denominator.

For laboratory tests where CTCAE grades are not defined, a shift table using the low/normal/high/(low and high) classification will be produced to compare baseline to the worst on-treatment value with each laboratory parameter on a new page. Percentages will be calculated using the number of available patients at baseline with corresponding level and at least one non-missing post baseline value as the denominator.

A frequency table will be created presenting number of patients with elevated liver chemistry tests based on worst post-baseline values for aspartate aminotransferase (AST), alanine aminotransferase (ALT), total bilirubin, and alkaline phosphatase parameters. Categories of elevated tests will be defined with regards to the upper or lower normal ranges, whichever is applicable. Percentages will be calculated using the number of patients in the safety analysis set.

A listing will be presented showing the visit sample date, laboratory number, laboratory name, albumin, SGOT (AST), SGPT (ALT), alkaline phosphatase, GGT, total bilirubin, direct bilirubin, indirect bilirubin, INR and PTT split by treatment.

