Visit Name	Category	Reference to Section 7.2	Screening Baseline	Core study																	End of core study/Early withdraw (EOS)	Safety FU visit **
				1	2	3	4	5	6	7	8	9	10	11	12	13	14	15	16	17		
Study Day			-28 to-1	1	15	21	29	49	57	85	113	141	169	197	225	253	281	309	337			
Week				2	3	4	7	8	12	16	20	24	28	32	36	40	44	48	52			
Contact IVRS for randomization			X																			
Pasireotide LAR injections (q28d)	D			X			X		X	X	X	X	X	X	X	X	X	X	X	X	X	X***
Everolimus administration (daily)	D			Daily***																		
Core study completion	D																				X	
*Only for patients treated with pasireotide LAR ** The safety FU visit should be performed only for patients who prematurely discontinue study treatment or experience disease progression at week 52. The visit should be performed 56 days after the last dose of pasireotide LAR or everolimus, whichever comes last. ***Pasireotide LAR injection and everolimus should be given at V18 only to patients that continue the extension phase																						

[figure not shown]
[figure not shown]

Table 7-2 EXTENSION PHASE - Visit evaluation schedule

Visit No.	Category	Reference to Section 7.2	Extension phase					End of extension phase /Early withdrawn	Safety FU visit**
			1	2	3	4			
Month of extension phase			3	6	9	12	Every 3 mos		
Vital signs	D	7.2.2.2	X	X	X	X	X	X	
Physical examination	S	7.2.2.1	X	X	X	X	X	X	
Weight	D	7.2.2.3	X	X	X	X	X	X	
WHO performance status	D	7.2.2.4	X	X	X	X	X	X	
Tumor evaluation, frequency at investigator's discretion***	D	7.2.1.1	X	X	X	X	X	X	
Gallbladder assessment, frequency as per tumor evaluation at investigator's discretion	D	7.2.2.6.4	X*	X*	X*	X*	X*	X*	
Pulmonary Function Test	D	7.2.2.6.2	As medically indicated						
Bronchoscopy	D	7.2.2.6.3	As medically indicated						
Chest X-ray, or Chest CT scan	D	7.2.2.6.1	As medically indicated						
ECG	D	7.2.2.7.1	X	X	X	X	X	X	
Cardiac imaging (ECHO or MUGA scan)	D	7.2.2.7.2	As medically indicated						
Hematology	D	7.2.2.5.1	X	X	X	X	X	X	
Biochemistry	D	7.2.2.5.3	X	X	X	X	X	X	
Fasting glucose/insulin/HbA1c (everolimus monotherapy)	D	7.2.2.5.4	X	X	X	X	X	X	
Fasting glucose/insulin/HbA1c (combination)	D	7.2.2.5.4	X	X	X	X	X	X	
Fasting glucose/insulin/HbA1c pasireotide LAR monotherapy	D	7.2.2.5.4	X	X	X	X	X	X	
Blood glucose self monitoring (if applicable)		7.2.2.5.4	Continuous						
Liver Function Tests	D	7.2.2.5.5	X	X	X	X	X	X	

[figure not shown]

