7.2.2.5.2 Coagulation

The international normalized ratio (INR) will be determined at screening/baseline, at Visits 2, 5, 7, 8 and every 8 weeks thereafter and reported in CRF. It will be determined also at Visits 4 and 6 for patients treated with pasireotide LAR. During the Extension phase, the INR will be

determined every three months. The partial thromboplastin time (PTT) will be determined only at screening/baseline.

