7.2.2.5.5 Liver Function Tests

The following tests will be performed at each scheduled visit (± 7 days during monthly visit period and ± 2 days during the weekly visit period) as indicated in [Table 7-1](#), and in [Table 7-2](#) and will include albumin, SGOT (AST), SGPT (ALT), total bilirubin (fractionate to direct/indirect bilirubin if total bilirubin is $> 2.0 \times$ ULN), alkaline phosphatase and GGT.

For patients treated with pasireotide LAR: the Day 21 and Day 49 LFTs should be available and assessed prior to dosing on Day 29 (2nd LAR injection) and Day 57 (3rd LAR injection).

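### Liver tests and INR are drawn twice more (Day 21, Day 49) in pasireotide-treated patients, and the SAP's worst-value liver tables by arm have no version limited to visits shared by all arms

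*SAP*

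**What the plan says.** **Schedule.** In Protocol Table 7-1 the LFT and INR entries at Visit 4 (Day 21) and Visit 6 (Day 49) carry an asterisk, explained in the footnote as "Only for patients treated with pasireotide LAR". Protocol 7.2.2.5.5 gives the purpose for LFTs: "the Day 21 and Day 49 LFTs should be available and assessed prior to dosing on Day 29", and likewise Day 49 before Day 57. For INR, Protocol 7.2.2.5.2 sets the common schedule "at Visits 2, 5, 7, 8 and every 8 weeks thereafter and reported in CRF" and adds the two pasireotide-only visits. SAP 10.4 repeats both rules; for INR it says "It will be determined also at Visits 4 and 6 for patients treated with pasireotide LAR".

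**Analysis.** SAP 10.4 plans shift tables for LFTs and INR "to compare baseline and the worst on-treatment value with each laboratory parameter on a new page". Their denominator is patients with the given baseline grade or level and at least one post-baseline value. It also plans a frequency table "presenting number of patients with elevated liver chemistry tests based on worst post-baseline values" for AST, ALT, total bilirubin and alkaline phosphatase, with the whole safety set as denominator. Protocol 10.5.3.1.1 presents all safety tables by study arm. Neither document limits these tables to visits common to the arms, adjusts for the number of draws, or carries a caveat.

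**The concern.** The worst of 16 values is at least as bad as the worst of 14 of the same values. With identical true liver risk in all arms, the schedule alone therefore pushes the two pasireotide-containing arms towards more abnormal worst values than everolimus monotherapy. Neither denominator removes this, because each counts patients and not draws. The two pasireotide-containing arms share a schedule, so the comparison between them is unaffected.

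SAP section 10 rests the safety assessment mainly on adverse events and laboratory abnormalities. Protocol section 10 and SAP 6.3.2 choose among successful arms on risk and benefit, and the Amendment 5 rationale reports that all three arms met the response criterion. In arms of 41 or 42, one or two patients with an uncommon liver elevation can change how a by-arm table reads.

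**Working it through.** **1. Scheduled draws after Day 1 (Protocol Table 7-1, 7.2.2.5.2, 7.2.2.5.5)**

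- LFT, all arms: Days 15, 29, 57, then every 28 days from 85 to 337 (10 draws), and Week 52. That is 3 + 10 + 1 = 14. With Days 21 and 49: 16.
- LFT through Day 85: Days 15, 29, 57, 85 = 4. With the extra two: 6.
- INR, all arms: Days 29, 57, 85, 141, 197, 253, 309 = 7. With the extra two: 9. Counting a Week 52 INR gives 8 and 10.
- INR through Day 85: 3 and 5.

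**2. Equal risk, independent draws**

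The documents give no per-draw probability *q* of an abnormal value and no figure on this point to reproduce. With *k* draws, P(worst value abnormal) = 1 - (1 - *q*)^*k*.

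| LFT, everolimus vs pasireotide-containing | *q* = 1% | *q* = 5% |
|---|---|---|
| Full core, *k* = 14 vs 16 | 13.1% vs 14.9% | 51.2% vs 56.0% |
| Through Day 85, *k* = 4 vs 6 | 3.9% vs 5.9% | 18.5% vs 26.5% |

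For INR over the core phase (*k* = 7 vs 9) at *q* = 1%: 6.8% vs 8.6%.

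**3. Equal risk, correlated draws**

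Independence exaggerates the gap, because each extra draw falls 8 days before a common one (21 before 29, 49 before 57) and a lasting elevation would be found there in every arm. The calculation was repeated by simulation (200,000 patients per setting). Values were Gaussian with the threshold set so that each draw exceeds it with probability *q*. Within-patient correlation was 0.5 or 0.8, either constant or with added short-term correlation that decays over 14 days. Ranges over *q* = 1% and 5%:

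| | Excess, points | Ratio | Patients in an arm of 41 |
|---|---|---|---|
| LFT, full core | 0.2 to 1.8 | 1.03 to 1.09 | 0.1 to 0.7 |
| LFT, through Day 85 | 0.4 to 4.2 | 1.12 to 1.37 | 0.2 to 1.7 |
| INR, full core | 0.3 to 3.0 | 1.07 to 1.21 | 0.1 to 1.2 |
| INR, through Day 85 | 0.5 to 4.8 | 1.19 to 1.53 | 0.2 to 2.0 |

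The last column is 41 times the excess; the Day 85 rows suppose that the whole arm stops there. The excess had the same sign in every setting.

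**4. Early stopping**

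The Amendment 5 rationale gives 43 of 124 randomized patients completing the core phase, so the shorter windows matter. Protocol 7.1.4 also asks patients who stop early for the end-of-core assessments. If that adds one LFT in each arm, a patient stopping near Day 85 has 5 vs 7 draws. At *q* = 1% and independence, 1 - 0.99^5 = 4.9% and 1 - 0.99^7 = 6.8%, a ratio of 1.39 instead of 1.49.

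**5. After restriction to common visits**

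Scheduled draws become 14 vs 14 for LFT and 7 vs 7 for INR (8 vs 8 with Week 52). The excess due to the schedule alone is then zero at equal risk and equal follow-up.

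**The case against.** The strongest reply is that the effect is small, its size is assumed, and using every collected safety value is a sound convention. That stands as regards size: over a full core phase the expected LFT excess under correlation is below one patient per arm. SAP 10.4 also states the extra draws in the section that defines the tables, and lists values by visit and sample date. The tables are rerun with extension data, where LFTs and INR follow one three-monthly schedule in all arms.

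Three stronger readings are tempting, and the documents do not support them.

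- *A large early excess.* Through Day 57 the LFT draws are 3 vs 5, which at 1% and independence gives 3.0% vs 4.9%. SAP 10.4 plans no table for the first eight weeks, so this matches no planned output.
- *A biased choice of arm.* The safety parameters that Protocol section 10 names are grade 3-4 adverse events, serious adverse events and treatment modifications. The liver tables are not named, and no between-arm safety test is planned. Extra draws could lead to more recorded adverse events or treatment changes, but filtering laboratory tables would not correct that.
- *The extra draws should be dropped from the comparison altogether.* Protocol 6.1.4.10 and 6.3.2.1 attach treatment interruption or discontinuation to defined elevations. Action on a Day 21 or Day 49 result may lower later values in the pasireotide arms, so a common-visit table alone could understate their liver events. Both versions are needed.

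What survives is the direction of the effect and the absence of any version that removes it.

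**Conclusion.** The point holds as a modest bias with a known direction. At equal true risk, the pasireotide-containing arms are expected to show slightly more abnormal worst liver values than everolimus monotherapy. The LFT ratio is about 1.03-1.09 over a full core phase and 1.12-1.37 for patients stopping near Day 85; the INR ratio is somewhat higher. Either way this is roughly 0-2 patients per arm of 41. INR is affected through the shift tables only, since the elevated-chemistry table does not include it.

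The draw counts come from the documents. The ratios rest on assumptions: 1-5% per draw, equal across arms and time; correlation of 0.5-0.8; one draw per scheduled visit; equal follow-up; and no unscheduled draws. A reader should not infer that an observed liver excess with pasireotide is an artefact of the schedule, because the documents give no rates from which to judge that. The primary endpoint is untouched.

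**What to change.** In SAP 10.4:

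1. Keep the shift tables and the elevated-liver-chemistry table on all draws, as planned.
2. Add a repeat of each, restricted to visits scheduled in all three arms (leaving out Day 21 and Day 49), and name it as the version for comparing everolimus monotherapy with the pasireotide-containing arms.
3. Footnote both versions with the unequal schedule. State that adverse event ascertainment is not corrected and that action taken on Day 21 or Day 49 results may lower later values in the pasireotide arms.

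The SAP already takes similar steps: repeat tables with exclusions in 5.3 (concomitant medication) and 10.5 (glucose, insulin, HbA1c), and in 10.10 a gallbladder shift table without the everolimus arm because those data are not collected there.

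The cost is one programming filter and one extra set of tables. The common-visit version leaves out some genuine early abnormalities, which remain in the all-draws tables and the listings. The safety draws themselves do not change.
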